#### DILI and CHF AEs

Incidence rates of all DILI and CHF AEs will be estimated, with two-sided 95% CIs. The diagnostic variables (eg, liver panel, echocardiogram, and/or CHF panel) at the time of each DILI or CHF diagnosis will be summarized descriptively.

SAEs, DILI, and CHF outcomes may also be treated as time-to-event endpoints and analyzed using survival analysis approaches. More details are provided in the SAP.

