#### Data analysis:

The analyses will be descriptive and presented separately for the omaveloxolone-naive cohort and non-naive cohort. Continuous variables will be described with summary statistics such as n, mean, standard deviation, median, first quartile, third quartile, and minimum and maximum values. For each categorical variable, the frequency and percentage will be reported.

Incidence rates will be calculated by dividing the number of new cases of SAEs (all) and all DILI and CHF AEs by the number of patient-years (PYs) at risk, which will be calculated over the follow-up period. In addition, 2-sided 95% confidence intervals (CIs) of incidence rates will be calculated.

There will be no imputation of missing data except for incomplete start dates for the purpose of time-to-event analyses.

A full annual report will be provided for EMA, and interim analyses on AEs of DILI and CHF are to be performed for the FDA biannually.

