#### Assumptions:

- Enrollment is estimated to be completed within 1 year.
- Each biannual report will include an additional 6 months of patient data, with the 1st biannual report forecast after 6 months of data collection and 3 months of report preparation.
- Data collection to end within 5 years after enrollment of Last Patient In.
- Final report forecast 6 months after final data collection.

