### 7.2.1 Safety profile

In Study 1402 Part 2 (pivotal trial), at least 1 treatment-emergent adverse event (TEAE) occurred in all (100%) omaveloxolone-treated patients and in all (100%) placebo-treated patients. The majority of TEAEs reported during the study were mild or moderate in intensity in both the treatment groups. The most common ( $\geq$  20% incidence in either treatment group) TEAEs with  $\geq$  5% difference in incidence in the omaveloxolone group compared with placebo were increased ALT (37.3% in the omaveloxolone group vs 1.9% in the placebo group), headache (37.3% vs 25.0%), nausea (33.3% vs 13.5%), fatigue (21.6% vs 13.5%), abdominal pain (21.6% vs 5.8%), and increased AST (21.6% vs 1.9%). Apart from increases in ALT and abdominal pain, a higher incidence ( $\geq$  5% difference) of these AEs in omaveloxolone patients compared with placebo patients was generally limited to the first 12 weeks of treatment as patients adjusted to omaveloxolone treatment and developed improved tolerability to the drug. These AEs were less frequently reported after Week 12.

Although drug-induced liver injury (DILI) and CHF are both listed as important potential risks in the proposed European Medicines Agency (EMA) risk management plan (RMP) for omaveloxolone (RMP for SKYCLARYS 150 mg capsules [omaveloxolone], data on file), as yet, there has been no report of DILI or CHF in association with the use of omaveloxolone in patients with FA.

Treatment with omaveloxolone has been associated with an increased incidence of ALT and aspartate aminotransferase (AST) elevations relative to treatment with placebo. Although no serious adverse events (SAEs) related to AST/ALT elevations were reported in clinical studies, it is important to follow any such AEs in the post-marketing setting and to monitor for potential occurrence of DILI.

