## 9.3.1 Primary outcomes

#### 9.3.1.1 Primary outcome definitions

The primary outcomes are the description and incidence of all DILI and CHF AEs and the description and incidence of all SAEs over time.

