## 9.4 Data sources

Medical information will be recorded in patients' medical records during every routine clinic visit and each time a laboratory test is performed (according to omaveloxolone labeling: monthly during the first 3 months of treatment, and periodically thereafter as clinically indicated; or per the UNIFAI study schedule of assessments). Additional timepoints can be defined if sufficient data are available. Patients' medical record information, research records, and any relevant diagnostic reports are the source documents for study data collection.

As all sites and patients are participating in the UNIFAI study, overlapping data will be extracted from the UNIFAI study where possible to avoid any additional burden to the investigators. When not collected by the UNIFAI study, clinical information recorded in patients' medical records and/or diagnostic reports will be abstracted and entered into the eCRF in the electronic data capture (EDC).

Each patient will have a unique number within the study (Patient Identification). Each site will maintain a Patient Identification list linking the patient to the Patient Identification within the study. Only the investigator and/or authorized personnel will be able to identify the patient based on the Patient Identification list, which will be held only at the site.

The MAH will be the "controller" of the personal data collected for the study. The MAH will take appropriate steps to ensure that personal data are protected.

All SAEs, regardless of causality, as well as pregnancy or lactation-related infant SAE data, will be reported to the MAH's safety vendor within 24 hours of the investigator's knowledge of onset or notification of the

Final protocol version date: 16 December 2024

event. More details on the SAE reporting can be found in Section 11. DILI and CHF AEs and lactation non-SAEs should be reported to the MAH's safety vendor within 7 days (Section 11.2.3.1).

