## 9.7.3 Descriptive statistics

Descriptive statistics will be used to summarize the study data in tables, listings, and figures as appropriate at baseline and post-index timepoints. These will cover descriptive analyses of patient demographics, clinical history, disease characteristics, clinical management, . The BDI-2 will be scored as per the developer's guidelines. Continuous variables will be described with summary statistics such as n, mean, standard deviation, median, first quartile, third quartile, and minimum and maximum values. For each categorical variable, the frequency and percentage in each category will be reported. Percentages will be calculated using the specified denominator in the table. The frequency and percentage of patients with missing data for each data point will be presented. Two-sided CIs of 95% will be calculated when relevant. Exact 95% CIs will be calculated assuming a Poisson distribution. Percentages will be reported with one decimal place.

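### The pooled DILI rate mixes patient time tested monthly with patient time scheduled for testing once a year, so it can fall across reports, or differ between cohorts, without a change in risk

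*Protocol*

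**What the plan says.** **Rate.** Section 9.7.4 (DILI and CHF AEs) says: "Incidence rates of all DILI and CHF AEs will be estimated, with two-sided 95% CIs". The Abstract (Data analysis) divides new cases "by the number of patient-years (PYs) at risk, which will be calculated over the follow-up period". Section 9.7.3 gives the interval method: "Exact 95% CIs will be calculated assuming a Poisson distribution". Results are shown separately for the naive and non-naive cohorts. No split by time on treatment is stated.

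**Outcome.** Section 9.3.1.1: "The primary outcomes are the description and incidence of all DILI and CHF AEs and the description and incidence of all SAEs over time". The same section leaves classification of a DILI AE to the investigator's judgment in normal practice.

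**Reports.** Section 6 lists twelve biannual DILI and CHF reports. The Abstract (Assumptions) adds: "Each biannual report will include an additional 6 months of patient data".

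**Testing.** Table 9-1 marks the liver panel at baseline and at months 1, 2, 3, 6, 12, 24, 36, 48 and 60. Section 9.4 describes label-driven testing as "monthly during the first 3 months of treatment, and periodically thereafter as clinically indicated". Section 9.2 says that data from assessments between timepoints are also collected.

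**Alternative analysis.** Section 9.7.4: "SAEs, DILI, and CHF outcomes may also be treated as time-to-event endpoints and analyzed using survival analysis approaches". Details are left to the SAP.

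**Limitations.** Section 9.9 covers selection, immortal time, recall and misclassification. It does not mention that liver testing thins with time on treatment.

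**The concern.** A rate per patient-year can be compared across calendar time or cohorts only if a case has a similar chance of being found in each patient-year. For a liver abnormality without symptoms, that chance depends on how often blood is drawn. The Abstract calls the ALT and AST rises seen with the drug transient. Section 7.2.1 exempts ALT from its statement that the early excess was generally confined to the first 12 weeks: that sentence opens "Apart from increases in ALT and abdominal pain, a higher incidence". Some detectable abnormality may therefore arise after scheduled testing has thinned.

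The early reports are dominated by densely tested months and the late ones by sparsely tested years. A falling cumulative rate could then be read as waning risk when it reflects fewer tests. The cohorts face the same problem side by side. Non-naive patients may enter up to 12 months after starting treatment and contribute no events from before enrollment (9.1.2), so their time lies largely in the thinly tested period. DILI is an important potential risk and part of a primary objective, so such a misreading would matter.

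**Working it through.** **1. The plan's own figure.** Table 9-5, N = 300, 5 years, rate 0.02: 30 events in 1,500 patient-years. The exact Poisson limits are χ²(0.025; 60)/2/1500 = 0.0135 and χ²(0.975; 62)/2/1500 = 0.0286. The table gives 0.013 and 0.029, so it reproduces. The table assumes one constant rate and reflects sampling error only.

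**2. Scheduled panels per patient-year (Table 9-1).** Panels in the window divided by its length in years:
- months 0-3: 3/0.25 = 12
- months 3-6: 1/0.25 = 4
- months 6-12: 1/0.5 = 2
- months 12-60: 4/4 = 1

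**3. Share of silent episodes caught.** Assume a constant true onset rate and an episode of length d that is found only if a scheduled panel falls inside it. The share caught is min(d, gap)/gap, where the gap between panels is 1, 3, 6 or 12 months. Four weeks = 28/30.4375 = 0.92 months.

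| Episode (assumed) | 0-3 | 3-6 | 6-12 | 12-60 | First/last |
|---|---|---|---|---|---|
| 4 weeks | 92% | 31% | 15% | 8% | 12.0 |
| 8 weeks | 100% | 61% | 31% | 15% | 6.5 |
| 12 weeks | 100% | 92% | 46% | 23% | 4.3 |
| 52 weeks | 100% | 100% | 100% | about 100% | 1.0 |

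If half of the 4-week episodes are found clinically, the first/last ratio is (0.5 + 0.5 × 0.92)/(0.5 + 0.5 × 0.077) = 0.96/0.54 = 1.8.

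**4. Effect on the cumulative rate.** Assume 300 naive patients enrolled uniformly over 12 months (the Abstract gives 1 year), with retention interpolated through the 260, 230 and 180 of Table 9-6. Weight each month on treatment by the patient time accrued, and count only panels done by the data cut. The share of patient time in months 0-3 on treatment falls from 76% at the 6-month cut to 6% at the 72-month cut. Crude rate as a fraction of the true rate:

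| Scenario | 6-month cut | 72-month cut | Fall |
|---|---|---|---|
| 4 weeks, scheduled panels only | 0.62 | 0.15 | 4.1-fold |
| 8 weeks, scheduled panels only | 0.67 | 0.25 | 2.7-fold |
| 12 weeks, scheduled panels only | 0.67 | 0.34 | 2.0-fold |
| 4 weeks, half found clinically | 0.81 | 0.57 | 1.4-fold |
| 4 weeks, 3-monthly panels after month 6 | 0.62 | 0.34 | 1.8-fold |
| 8 weeks, 3-monthly panels after month 6 | 0.67 | about 0.63 | nearly flat |
| 52 weeks, scheduled panels only | 0.67 | above 0.95 | none; it rises |

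The 6-month values lie below the window shares in step 3 because some episodes begin after the last panel before the cut.

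**5. Event counts.** The 6-month cut holds about 37 patient-years. At the Table 9-5 rates of 0.01 to 0.05 that is 0.4 to 1.9 true events, so the first report can show little. The 12-month cut holds about 143 patient-years. From there, the 4-week case falls from 0.47 to 0.15, about 3-fold.

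**The case against.** The strongest objection is that DILI here is not a silent ALT rise. Section 9.3.1.1 requires a clinically significant abnormality that would be worked up in normal practice. Section 7.2.1 reports raised ALT in 37.3% of treated patients in the pivotal trial, yet no DILI. That trial part lasted 48 weeks, so it says nothing about months 12-60. This stands: the size depends on how many DILI AEs are silent and short, and the documents do not say.

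Second, a reader might infer that patients are tested only once a year after month 12. They need not be. That is the scheduled level; further tests follow clinical indication, their results are collected (9.2, 9.4), and patients are encouraged to report events between visits (9.3.1.2). This also stands, and it shrinks or removes the effect in some scenarios. But unscheduled testing will vary, and nothing in 9.7.4 relates the rate to it.

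Third, no trend test or formal comparison between reports or cohorts is planned, and 13.2 promises biannual interim analyses without naming the measure. In 9.3.1.1 the words about time directly follow SAEs and only arguably cover DILI. True, but the pooled rate is the only DILI incidence measure defined, and readers of successive reports will compare its values.

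Fourth, much of this could be SAP detail. That is fair for the dating of onsets in an optional survival analysis, which is not part of this point. Such an analysis would show timing but would not by itself undo unequal detection. Recording how a case was found must be settled at data collection, and 9.3.1.2 lists no such item.

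**Conclusion.** The point holds in a limited form. The protocol fixes one DILI rate over follow-up whose chance of finding silent cases changes with time on treatment, and neither 9.7.4 nor 9.9 deals with it. In naive patients, with silent events of 4 to 12 weeks found only by scheduled panels, the detected share falls about 2- to 4-fold between the first and last data cuts at constant risk. More clinical detection, more frequent testing or longer abnormalities reduce this to about 1.4-fold, to almost nothing, or reverse it.

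A reader might infer that the rate must fall by construction, or by the 12-fold drop in scheduled panels. The documents do not support either: both need events that are silent, shorter than the test gap and found by scheduled panels alone. Event duration, clinical share and extra testing are assumptions. What the documents do show is that a decline, or a cohort difference, could not be interpreted from the planned rate alone. This is a worthwhile, low-cost improvement rather than a flaw that invalidates the study.

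**What to change.** In 9.7.4, for each cohort and each report:

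1. Give DILI rates by time on treatment (0-3, >3-6, >6-12 and >12 months), beside the liver panels actually performed per patient-year in each window, scheduled and unscheduled.
2. Show serious or symptomatic DILI separately from panel-detected DILI. Seriousness is already recorded; add one mode-of-detection item to the DILI form.
3. Make any statement on trend or cohort difference within the same time-on-treatment window, or on the serious or symptomatic group.

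In 9.9.2.1, name detection that depends on test frequency as a bias.

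The cost is protocol wording, a few tables and one form item. No test or visit is added, and panel results are already collected. The downside is fewer events and wider intervals in each window, so the pooled rate should stay beside the split rates.

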			Extended safety follow- up from 30 to 60 days	Change made based on regulatory feedback				
			Clarified current vs new users and associated analyses	Based on timing of launch of omaveloxolone				

Protocol Amendment Version Number	Version Date	Protocol Section	Summary of Relevant Updates	Reason				
			Removed the restriction on current users to only include patients who had started omaveloxolone within the 6 months prior to enrollment					
		11. Management	Updated to describe general standards	Removal of previously planned safety vendor				
		and reporting of adverse events	Extended safety follow- up from 30 to 60 days	Change made based on regulatory feedback				
		12. Protocol deviations	Added section on protocol deviations	As requested by investigators				
		13. Plans for results	Clarified data ownership	Not applicable				
	Throughout	Current omaveloxolone users will no longer be allowed to enroll, which affected language throughout the protocol (eg, no longer any need for sensitivity analyses).	Adverse events that occur commonly in the first 12 weeks of treatment would not be captured if current users are allowed to enroll (ie, the first 12 weeks will have already passed).					
		Throughout	Only patients who discontinue the study or treatment are required to attend the 60-day safety follow-up visit.	Clarification to ensure that patients who complete the study are not required to return after 60 months.				
Amendment 2 (version 3.0)	04 March 2024	Throughout	Removed alkaline phosphatase, gammaglutamyl transferase, direct bilirubin, and indirect bilirubin from liver panel.	These laboratory tests are not required as part of the liver panel, per labeling recommendations.				
		Throughout	Added lipid panel: LDL, HDL, and triglycerides	These laboratory tests are required per labeling recommendations.				
			Removed Table 9-1.	Information was redundant to the schedule of assessments.				
		9.2 Setting	Separated the schedule of assessments into Tables 9-1, 9-2, and 9-3.	Per request from key medical experts (KMEs), assessments were separated to indicate which assessments are required per protocol/label, which are				

Protocol version of Protocol Amendment Version Number	Version Date	Protocol Section	Summary of Relevant Updates	Reason			
				optional, and which are already covered in UNIFAI.			

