# 9.2 Setting

This study is strictly observational; the assignment of patients to omaveloxolone or any drug will not be determined in advance by the protocol and will be clearly separated from the decision to include the patients in the study. The treating physician will determine the patient visits and assessments according to routine practice and as per the relevant approved product label (eg, USPI or European Union [EU] SmPC). The schedule of assessments proposed in this study is based on anticipated visits as per the prescribing label and as per the UNIFAI study. No additional in-person visits are expected solely for this omaveloxolone study. The plan is to collect as much information as possible without imposing any additional burden on patients and families.

Data from all routine clinical care assessments that occur during the follow-up period will be collected and analyzed by specified timepoints: at 1 month, 2 months, 3 months, 6 months, 12 months, 24 months, 36 months, 48 months, and 60 months. A 60-day safety follow-up visit is required for patients who discontinue omaveloxolone treatment or discontinue from the study (unless discontinued due to death or withdrawal of consent). These timepoints approximately match the routine follow-up for patients initiating omaveloxolone treatment and/or the annual visits for the UNIFAI study. If any additional assessments occur between these timepoints, these data will be collected via additional forms.

Table 9-1 presents the schedule of assessments to be collected solely for this study. Table 9-2 presents the schedule of optional assessments, which are not specified per prescribing label but may be requested by the prescribing/treating physician. The schedule of assessments collected per the UNIFAI study is presented in Table 9-3.

Table 9-1. Schedule of assessments for this PASS

	Baseline a	1 b	2 b	3 b	6 b	12	24	36	48	60° (EOS)	60-Day Discon Follow-up c (EOS)
History of depression (Beck Depression Inventory)	Χq										
Adverse event data collection	Х	X	Χ	Χ	Χ	Χ	Χ	Χ	Х	Х	Х
Treatment data collection	Х	Х	Х	Х	Χ	Χ	Χ	Χ	Χ	Х	
Liver panel b,e : ALT, AST, TBL	Х	Х	Х	Х	Х	Χ	Х	Х	Х	Х	

Final protocol version number: 6.0

Final protocol version date: 16 December 2024

	Baseline a	1 b	2 b	3 b	6 b	12	24	36	48	60° (EOS)	60-Day Discon Follow-up c (EOS)

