#### **DILI and CHF AEs**

Any clinically significant abnormality in liver function that would be evaluated as a potential DILI event as part of normal clinical practice based on the judgment of the investigator may be considered (as described in Section 11.2). As a guide, AEs that will be considered a DILI AE by the investigator are generally events that fall within the MedDRA System Organ Class (SOC) Hepatobiliary disorders, but classification of events is at the discretion of the investigator. As per the omaveloxolone prescribing label, if transaminases increase to levels > 5X ULN, or > 3X ULN with evidence of liver dysfunction (eg, elevated bilirubin), the treating physician must immediately discontinue the drug and repeat liver function tests as soon as possible. If transaminase levels stabilize or resolve, omaveloxolone may be reinitiated with an appropriate increased frequency of monitoring of liver function.

Any clinically significant abnormalities in cardiac function that would be evaluated as a potential CHF event as part of normal clinical practice based on the judgment of the investigator may be considered (as described in Section 11.2). For example, a CHF event may be defined as a New York Heart Association (NYHA) class III or IV or death related to CHF utilizing the Standardized MedDRA Query (SMQ) cardiac failure. As a guide, AEs that will be considered a CHF AE generally include events that fall within the MedDRA High Level Group Term (HLGT) of Heart failures, including the High Level Terms (HLTs) of Heart failure signs and symptoms, Heart failures Not Elsewhere Classified, Left ventricular failures, and Right ventricular failures, but classification of events is at the discretion of the investigator. As per the omaveloxolone prescribing label, monitoring patients for the signs and symptoms of fluid overload, such as sudden weight gain (3 pounds or more of weight gain in one day, or 5 pounds or more of weight gain in a week), peripheral edema, palpitations, and shortness of breath is recommended. If signs and symptoms of fluid overload develop, worsen, or require hospitalization, evaluation of BNP (or NT-proBNP) and cardiac function and management by the treating physician in accordance with medical practice is recommended. Management of fluid overload and heart failure may require discontinuation of the drug.

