#### Outcome variables related to DILI and CHF include:

- Start and end dates of the AE
- Outcome of the AE
- Action(s) taken with omaveloxolone treatment by the treating physician
- Causal relationship to omaveloxolone treatment (per investigator)
- Severity of the AE
- Seriousness of the AE
- Date of AE treatment initiation by the treating physician
- Lipid panel
  - Low-density lipoprotein (LDL)
  - High-density lipoprotein (HDL)
  - Triglycerides
- Signals for DILI at time of DILI diagnosis, as applicable
  - Liver panel
    - Serum aminotransferases
      - ALT
      - AST
    - TBL
- Signals for CHF at time of CHF diagnosis, as applicable
  - Date of AE treatment initiation by the treating physician
  - Electrocardiogram
  - Echocardiogram
  - Cardiac magnetic resonance imaging (MRI), if available
  - CHF panel
    - B-type natriuretic peptide (BNP) and/or
    - N-terminal prohormone B-type natriuretic peptide (NT-proBNP)

Information on all DILI and CHF AEs and all SAEs will be collected, and patients will be encouraged to contact their treating physician in between visits as per routine clinical practice to report any potential events.

Final protocol version number: 6.0

Final protocol version date: 16 December 2024

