## 9.6.2 Data monitoring

was chosen as the EDC platform, in part, to avoid duplicative training as site staff are already trained in the use of systems. Specific guidance on the data collection in this study are covered in the eCRF Completion Guidelines.

Final protocol version date: 16 December 2024

The CRO or designee (Section 14) will supervise and perform remote site management and monitoring, as described in the study-specific data management plan (Data Validation Manual) and the site monitoring plan. All participating sites will only have access to view and enter the data for their own patients. Only data required by the protocol for the purposes of the study should be collected.

All data entries in the study-specific EDC will be reviewed for clarity, uniqueness (non-duplication), completeness, and coherence in accordance with the data management plan (Data Validation Manual), edit checks, and manual queries. Missing, inconsistent, or unclear data will be queried as necessary throughout the study. Sites will be responsible for responding to queries in a reasonable timeline. The CRO or designee will also be responsible for the quality control of the study-specific database and confirming the overall integrity of the study-specific data. Quality-control mechanisms (eg, verification of data completeness, validations, skip-logic, and edit checks) are built into the EDC and employed at the time of data entry. Queries will be generated for resolution by site staff within the EDC system. The EDC system has built-in methods for data validation (eg, drop-down lists, value range controls, and standardized response formats) to minimize data entry errors; however, a data cleaning method will be employed to correct inconsistencies or errors that were not captured during data entry (eg, outliers or inconsistent data). Data queries will be identified on an ongoing basis during data collection. Sites will receive a regular e-mail notifying them of any new or outstanding queries. Formal source data verification is not expected in this study.

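### The planned laboratory summary of DILI events stops at ALT, AST and TBL at diagnosis, so it is a lower bound on peak injury and cannot give the injury pattern

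*Protocol*

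**What the plan says.** Protocol section 8.2.1 makes documenting and characterising all DILI and CHF adverse events a primary objective. For the liver data attached to an event, section 9.3.1.2 has the entry "Signals for DILI at time of DILI diagnosis, as applicable", under which it names ALT, AST and TBL. The primary analysis in section 9.7.4 takes the same moment: "The diagnostic variables (eg, liver panel, echocardiogram, and/or CHF panel) at the time of each DILI or CHF diagnosis will be summarized descriptively". The only other laboratory analysis, in section 9.7.5, is the change from baseline using the entry nearest each scheduled timepoint.

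Other provisions bear on the point:

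- **Non-laboratory event data.** Section 9.3.1.2 also collects start and end dates, outcome, action taken, causality, severity, seriousness and the date treatment of the event began. Section 11.2.2 adds a description and other possible causes.
- **Tests between scheduled visits.** Section 9.2: "If any additional assessments occur between these timepoints, these data will be collected via additional forms".
- **Repeat testing.** Section 9.3.1.1 relays label text under which, after a marked transaminase rise, "the treating physician must immediately discontinue the drug and repeat liver function tests as soon as possible".
- **Follow-up.** Sections 11.2.3.1 and 11.2.3.2 ask for follow-up to resolution or stabilization.
- **Panel content.** Table 9-1 defines the liver panel as ALT, AST and TBL. As background consistent with the current text, the amendment log for version 3.0 records: "Removed alkaline phosphatase, gammaglutamyl transferase, direct bilirubin, and indirect bilirubin from liver panel", because labeling did not require them.
- **Limit on data entry.** Section 9.6.2: "Only data required by the protocol for the purposes of the study should be collected".

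**The concern.** Section 7.2.1 explains why DILI is followed: transaminase elevations were more frequent on omaveloxolone than on placebo, and the study is to watch whether any becomes liver injury. Answering that needs the height of the transaminase rise, whether bilirubin rose with it, and the pattern of injury. A single panel at diagnosis gives the first two only as they stood at that moment, and the third not at all.

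The laboratory values carry much of the objective evidence here. Section 9.3.1.1 leaves classification as DILI to the investigator's discretion, the protocol describes no adjudication, and section 9.6.2 does not expect formal source data verification. If the report shows only diagnosis values, a regulator cannot see how far each case went, even where later results are in the database.

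**Working it through.** No sample size, power or error rate is involved, so the check sets the provisions side by side.

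**1. Which time point is fixed?** Sections 9.3.1.2 and 9.7.4 both tie the event's liver values to the time of diagnosis. The wording in 9.7.4 leaves the list of variables open by giving examples, but not the time point. Section 9.7.5 uses the entry closest to each visit. Neither rule selects an episode maximum.

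**2. What follows for the size of the values?** Let D be the value at diagnosis and P the maximum from onset to resolution. D is one of the values over which P is taken, so P ≥ D for each of ALT, AST and TBL. Equality holds only if the event was diagnosed at its peak. The planned summary is therefore a lower bound on peak values. The gap P − D depends on when diagnosis is made and how the injury evolves; the documents give neither.

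**3. Does the protocol expect later values?** Yes, for events that trigger the label text in 9.3.1.1: it asks sites to "repeat liver function tests as soon as possible". Section 9.2 collects all routine assessments within follow-up, with unscheduled ones on extra forms. Peak values can thus be derived wherever repeat tests were done; they are simply not named as an output. There is no scheduled backstop after stopping: the liver-panel row of Table 9-1 is blank at the 60-day discontinuation visit, and section 9.3.5.3 lists no laboratory value there. Values after stopping then rest on the unscheduled forms.

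**4. Can severity stand in for peak values?** Section 11.1.5 grades by discomfort, effect on functioning and need for treatment. A large transaminase rise without symptoms can be graded mild. Section 9.7.4 tabulates treatment-emergent serious events by severity and states no such table for non-serious DILI events.

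**5. Can the injury pattern be derived?** Separating hepatocellular from cholestatic injury needs ALP set against ALT. The defined panel has no ALP. Nor does it have direct bilirubin or INR, so bilirubin fraction and synthetic function are also out of reach.

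**6. Can the effect be sized from Table 9-5?** At 300 patients for 5 years the table gives 1,500 patient-years × 0.01 = 15 events and × 0.05 = 75 events. These combine DILI and CHF, use rates the protocol calls hypothetical, and assume no attrition, whereas Table 9-6 anticipates 180 patients completing five years. They yield neither a DILI count nor an amount of understatement.

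**The case against.** Two stronger readings are tempting, and the documents do not support them.

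- **That DILI events are characterised only by these three tests.** They are not. Seriousness, severity, outcome, dates, action taken and causality are recorded for every event, with a description and follow-up to resolution or stabilization. The limit applies to the laboratory values summarised.
- **That severe cases will be reported as milder than they were.** Severity is graded by the investigator and not read from the diagnosis panel, and section 11.1.2 asks for it to be assessed independently. Serious events are tabulated by severity. Nor is the time of diagnosis defined as the first abnormal test; it may follow repeat testing, and then the gap could be small or nil.

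The best remaining argument is that peak values are ordinary SAP content, that section 9.7 leaves detail to the SAP, and that nothing in 9.7.4 forbids them. That is fair as regards peak ALT, AST and bilirubin: the data should largely exist, and the SAP could add the summary. But the protocol does state a time point for a primary outcome, and it is the less informative one. The SAP also cannot recover ALP that the forms do not ask for.

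The removal of ALP and bilirubin fractions was a reasoned decision about the routine panel, in a study meant to add no burden. That stands, and it is a reason to leave the routine panel alone. It does not argue against recording a result already on the local report of a DILI case. Section 9.6.2 does not expressly bar such results, given the broad collection in 9.2 and the open list in 9.7.4, but no field is defined for them.

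**Conclusion.** The point holds as a limit of the planned laboratory summary. As written, sections 9.3.1.2 and 9.7.4 describe each DILI event's biochemistry by ALT, AST and TBL at diagnosis. These values are a lower bound on peak injury, and the defined panel cannot yield hepatocellular versus cholestatic pattern. The recorded severity, seriousness, outcome and dates are useful but do not replace laboratory values, because the severity scale rests on symptoms.

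The size of the understatement cannot be given. It would need the timing of diagnosis relative to peak and the frequency of repeat testing, and the documents contain neither. The lower-bound statement needs no clinical assumption; how much it matters depends on how often values rise after diagnosis. This is a cheap improvement to a primary outcome, not an error that invalidates the planned incidence rates, which are unaffected.

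**What to change.** **Sections 9.3.1.2 and 9.7.4.** For each DILI event, report the value at diagnosis and the peak ALT, AST and TBL from onset to resolution or stabilization, each as a multiple of the local ULN. Table 9-1 allows samples to be taken at local laboratories, so raw values are not directly comparable. Add time to peak and a per-case listing showing transaminases and bilirubin together. Use the repeat tests already collected under section 9.2, and state how many events had any test after diagnosis, so that a peak equal to the diagnosis value can be read correctly.

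**DILI event form only.** Add fields for ALP, INR and direct bilirubin with their local ULN, to be completed where they were measured locally. Naming these fields in the protocol makes them protocol-required data under section 9.6.2. The routine panel in Table 9-1 does not change.

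**Optional parallel.** Give peak BNP or NT-proBNP for CHF events, by analyte, since section 9.7.4 uses the same single time point for them.

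**Cost.** A few event-form fields, one listing and a little more abstraction per event. No test or visit is added. The first patient has already been enrolled, so the fields are best added early.
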